4.3 Blinding

Study site staff, except for the site Pharmacist of Record or their designee, and participants will be blinded to the random assignments. Blinding will be maintained until the trial is completed or stopped, i.e., the trial is stopped early, or the required number of endpoints (114) has been met. At a specified time directed by the HPTN Statistics and Data Management Center, participants will be notified of their treatment assignment.

In addition, as described in sections 5.14 and 5.18 of the HPTN Protocol 084, v2.0, participants with a confirmed pregnancy will be unblinded. Participants who are unblinded due to pregnancy may restart open-label study product in their original randomization arm (open label CAB LA or TDF/FTC) following delivery and cessation of breastfeeding.

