Data from steps 1 and 2 (PRIMARY mITT dataset) will be used. Tables will summarize the number of pregnancies and pregnancy rate by arm. The pregnancy rate and 95% robust confidence interval for each treatment arm will be calculated using a log-linear model for counts using log(person-time) (excluding time spent pregnant) as an offset, assuming a Poisson distribution, and using a robust variance (i.e. generalized estimating equations).

Outcomes of all detected pregnancies (PREGNANCY dataset) and all confirmed pregnancies (CONFIRMED PREGNANCY dataset), including information of drug exposure during the conception period and pregnancy period, will be tabulated by arm.

e. **Objective:** To evaluate rates of HIV drug resistance among participants who acquire HIV infection during the study among participants receiving oral CAB/CAB LA vs. oral TDF/FTC.

Population: Primary SEROCONVERTER Population

Data from steps 1, 2 and 3 will be included. The number of cases of drug resistance will be summarized by arm and step. All cases of drug resistance among incident HIV infections during the study will be described.

f. **Objective:** To determine plasma concentrations of medroxyprogesterone (DMPA) or norethisterone (NET-EN) or etonorgestrel (from implants) when co-administered with CAB LA.

Population: CONTRACEPTION Subgroup Population

Outcome: Plasma concentration of medroxyprogesterone or norethisterone.

Boxplots of plasma concentrations of DMPA/NET_EN/etonorgestrel will be generated by arm. For women in the CAB-LA arm, a plot of plasma concentrations versus time since last injection will be plotted and a smooth line will be fit through the data. Proportion of women with plasma concentrations below 0.1 ng/mL (DMPA) or TBD (NET_EN) or 90pg/mL (etonorgestrel) will be reported and compared (separately, for women using each drug) between arms using a Fisher's exact test or a permutation test if multiple observations are available on each woman.

In addition, we will compare mean contraceptive drug levels (and/or other PK parameters) between the CAB LA and TDF/FTC arms for each contraceptive subgroup using a t-test (or a t-test with robust variance if multiple observations on each woman are available).

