9.2. Clinical Study Report

The tables described below will be included in the CSR. Additional tables and analyses may be included, at the discretion of the protocol team or sponsor, e.g., depending on the availability of additional laboratory evaluations. All reports and analyses will be presented by study arm.

Subjects will be pooled across all sites. Data will be presented by treatment group and overall. Categorical variables will be summarized by frequency distributions (number and percentages of subjects) and continuous variables will be summarized by descriptive statistics (mean, standard deviation, etc.).

Adverse events will be summarized by treatment group using the Medical Dictionary for Regulatory Activities (MedDRA) system organ class and preferred term. Tabulations will be produced for all treatment-emergent AEs (TEAEs) defined as AEs with an onset date on or after the start of treatment, treatment-related AEs (those considered by the Investigator as at least possibly drug related), SAEs, discontinuations due to AEs, and AEs by severity grade. By-subject listings will be provided for any deaths, SAEs, and AEs leading to discontinuation.

Descriptive statistics for each treatment group will be provided for clinical laboratory values (e.g., hematology, serum chemistry, and urinalysis) and vital signs data, presented as both actual values and changes from baseline relative to each on-study evaluation. Abnormal clinical laboratory values will be listed. All data will be provided in by-subject listings.

Displays of the cumulative incidence of events such as HIV infection, or treatment discontinuation, will include at-risk tables as follows: Numbers of subjects having had the event of interest, and at risk to have had the event will be shown at selected weekly timepoints under the horizontal axis. The number at risk will be computed as the number of subjects with event times greater than or equal to the given timepoint

- **Subjects Disposition**

The subject disposition summary will include the number screened, the number of screen failures, the number enrolled, the number in each patient population for analysis, the number who completed the study, the number who discontinued the study and reason for discontinuation from the study.

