APPENDIX E – Adverse Events of Special Interest

Adverse events of special interest (AESI) have been determined for CAB based on pre-clinical and clinical experience, along with information for the integrase inhibitor class of HIV medications safety profile. These are adverse events for which more detailed summaries of event characteristics are of interest. Details of the analyses of AESI are contained in Section **Error! Reference source not found.** based on the current MedDRA version used for the study, v23.1.

The identification and classification of AESI will have occurred as a clinical review of preferred terms for adverse events, lab data, ECG and vital signs prior to the unblinding of the studies. (see Appendix E Section 1).

Table 1 shows the adverse events of special interest identified and reasons for including.

Table 1 Adverse Events of Special Interest

AESI	Product Implicated	Reason for Including as AESI
Hepatic Safety Profile: Assessment of risk of hepatotoxicity	CAB	Clinical, Class, Regulatory Interest,
Hypersensitivity Reactions (HSR)	CAB	Class, Regulatory Interest,
Rash	CAB	Class, Regulatory Interest
Neuropsychiatric Events 
 • Suicidal Ideation/Behaviour • Depression • Bipolar Disorder • Psychosis • Mood Disorders • Anxiety • Sleep Disorders 	CAB	Clinical, Class, Regulatory Interest,
Injection Site Reactions (ISR)	CAB	Clinical, Regulatory Interest
Seizures and Seizure-like events	CAB	Clinical, Regulatory Interest
Weight Gain	CAB	Clinical, Class, Regulatory Interest
Rhabdomyolysis	CAB	Clinical, Class, Regulatory Interest
Pancreatitis	CAB	Clinical, Therapeutic Area, Regulatory Interest

Impact on Creatinine	CAB	Regulatory Interest, Therapeutic Area
Safety in Pregnancy (Does not apply to HPTN083)	CAB	Regulatory Interest, Class
Hyperglycaemia/new onset diabetes mellitus	CAB	Observation from 083, Class

Common ISR adverse events are defined by MedDRA preferred terms including injection site pain, injection site induration, injection site nodules and preferred terms of any other ISR with $\geq 5\%$ participants in either treatment arm. ISRs are summarized and listed regardless of IP relationship.

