Dyssomnia	10061827
Exploding head syndrome	10080684
Hypersomnia	10020765
Hypersomnia related to another mental condition	10020767
Hypersomnia-bulimia syndrome	10053712
Hypnagogic hallucination	10020927
Hypnopompic hallucination	10020928
Hyposomnia	10067530
Initial insomnia	10022035
Insomnia	10022437
Insomnia related to another mental condition	10022443
Irregular sleep phase	10022995
Irregular sleep wake rhythm disorder	10080301
Loss of dreaming	10065085
Middle insomnia	10027590
Narcolepsy	10028713

Nightmare	10029412
Non-24-hour sleep-wake disorder	10078086
Parasomnia	10061910
Paradoxical insomnia	10083337
Periodic limb movement disorder	10064600
Pickwickian syndrome	10035004
Poor quality sleep	10062519
Rapid eye movement sleep behaviour disorder	10077299
Rapid eye movements sleep abnormal	10037841
Shift work disorder	10078088
Sleep apnoea syndrome	10040979
Sleep attacks	10040981
Sleep disorder	10040984
Sleep disorder due to a general medical condition	10063910
Sleep disorder due to general medical condition, hypersomnia type	10040985
Sleep disorder due to general medical condition, insomnia type	10040986
Sleep disorder due to general medical condition, mixed type	10040987
Sleep disorder due to general medical condition, parasomnia type	10040988
Sleep inertia	10067493
Sleep paralysis	10041002
Sleep sex	10067492
Sleep talking	10041009
Sleep terror	10041010
Sleep-related eating disorder	10067315
Somnambulism	10041347
Somnolence	10041349
Somnolence neonatal	10041350
Sopor	10058709
Stupor	10042264
Terminal insomnia	10068932
Upper airway resistance syndrome	10063968

Injection site Reactions

Use CRF terms for ISR.

Safety in Pregnancy (084 only)

Use AE terms co-reported in pregnancy exposures to CAB.

Seizures/Convulsions

PT	PT Code
1p36 deletion syndrome	10082398
2-Hydroxyglutaric aciduria	10078971
Acquired epileptic aphasia	10052075
Acute encephalitis with refractory, repetitive partial seizures	10076948
Alcoholic seizure	10056347
Alpers disease	10083857
Aspartate-glutamate-transporter deficiency	10079140
Atonic seizures	10003628
Atypical benign partial epilepsy	10056699
Automatism epileptic	10003831
Autonomic seizure	10049612
Baltic myoclonic epilepsy	10054895
Benign familial neonatal convulsions	10067866
Benign rolandic epilepsy	10070530
Biotinidase deficiency	10071434
CEC syndrome	10083749
CDKL5 deficiency disorder	10083005
Change in seizure presentation	10075606
Clonic convulsion	10053398
Congenital bilateral perisylvian syndrome	10082716

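### The pregnancy AESI draws its terms only from CAB-exposed pregnancies, with no list or stated source; if those are this trial's CAB-arm pregnancies, the summary is one-sided

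*SAP*

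**What the plan says.** SAP Appendix E, Section 1, gives the pregnancy item, tagged as applying to this trial only, a single instruction: "Use AE terms co-reported in pregnancy exposures to CAB". No preferred terms, codes or dataset follow.

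The rest of the section is built differently. The other AESI have printed preferred-term lists with MedDRA codes, except injection site reactions, which use CRF terms. The opening of the appendix also has a data-driven rule for common injection site reactions, and it admits a term that reaches its threshold in whichever arm.

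On origin, the appendix says "Adverse events of special interest (AESI) have been determined for CAB based on pre-clinical and clinical experience". On timing, it describes a clinical review of "preferred terms for adverse events, lab data, ECG and vital signs prior to the unblinding of the studies". On method, it says "Details of the analyses of AESI are contained in Section", and the section number is a broken cross-reference. Its Table 1 lists safety in pregnancy as of regulatory interest and names CAB as the product implicated.

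Three other places bear on the point:
- Section 4.3: "participants with a confirmed pregnancy will be unblinded".
- Section 7.3.7 d: outcomes of all detected and all confirmed pregnancies, "including information of drug exposure during the conception period and pregnancy period, will be tabulated by arm".
- Section 9.2, for the Clinical Study Report: "All reports and analyses will be presented by study arm".

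**The concern.** A term set for a safety summary should not depend on which arm the events occurred in. Here the only stated source is pregnancies exposed to one product. If that means CAB-arm pregnancies in this trial, there are two ways to follow the rule. The summary can cover CAB exposures only, and then it has no TDF/FTC counterpart. Or the terms can be applied to both arms, and then every term has at least one CAB event by definition, while a term reported only in TDF/FTC pregnancies cannot appear.

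Under section 2.7.4 every pregnant participant receives open-label TDF/FTC, whichever arm she was randomized to. Pregnancies in the TDF/FTC arm are therefore the natural reference for prior or residual CAB exposure. A one-sided term set leaves that reference unused or filters its events through what happened on CAB, in a summary that the SAP itself marks as of regulatory interest.

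**Working it through.** **Is there a figure to reproduce?** No. The SAP states no number for this AESI and no expected count of pregnancies or of adverse events in pregnancy. The calculation below only shows the direction of the effect and its possible size.

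**Inputs.**
- Allocation 1:1 (section 4.2).
- Term source: CAB-exposed pregnancies (Appendix E, Section 1).
- Assumption A: the terms are taken from this trial's CAB-arm pregnancies.
- Assumption B: the same terms are then counted in both arms.
- Assumption C: no drug effect, with independent Poisson counts of equal mean m per term in each arm. The SAP does not give m, so a range is shown.

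**Formula.** A term is kept only if its CAB count is at least 1.
- Expected CAB events kept per term: m, because discarded terms have no CAB events.
- Expected TDF/FTC events kept per term: m × (1 − exp(−m)), because the TDF/FTC count is independent of the selection.
- Ratio of expected counts, CAB:TDF/FTC = 1 / (1 − exp(−m)).
- Share of TDF/FTC events dropped = exp(−m).

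For m = 0.5: exp(−0.5) = 0.607, 1 − 0.607 = 0.393, and 1/0.393 = 2.54.

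| m per term per arm | CAB:TDF/FTC ratio | TDF/FTC events dropped |
|---|---|---|
| 0.1 | 10.5 | 90% |
| 0.25 | 4.5 | 78% |
| 0.5 | 2.54 | 61% |
| 1 | 1.58 | 37% |
| 2 | 1.16 | 14% |
| 3 | 1.05 | 5% |
| 5 | 1.01 | 0.7% |

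Simulation of one million terms at each m agrees with the formula (for example 2.55 at m = 0.5 and 1.16 at m = 2).

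**Relaxing assumption C.** Real terms do not share one frequency. With gamma-distributed term means (shape 0.3 to 5), the simulated ratio is:
- 1.38 to 2.30 at an average of 0.5 events per term
- 1.18 to 1.50 at an average of 1
- 1.08 to 1.15 at an average of 2

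The direction does not change. The size falls, because frequent terms are kept anyway and carry most of the events.

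**With an arm-neutral term set.** If the terms are fixed without regard to arm, or are the union of terms from pregnancies in both arms, the expected ratio under no drug effect is 1.00 at every m.

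**The case against.** The strongest answer is that the line need not refer to this trial's data. Appendix E bases its AESI on earlier CAB experience and speaks of the unblinding of several studies. Its Table 1 notes that the pregnancy row does not apply to a sister trial, so the text looks shared across a programme. If the terms were fixed from earlier CAB experience, nothing is selected on this trial's outcomes and the ratios above do not arise. This stands, and for this reason the documents do not support a reader's inference that the summary is biased against CAB by construction. What it leaves open is that no such list is printed, although the other term-based AESI have theirs, and that the item is tagged for this trial only. On either reading the line does not fix a term set.

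A reader might also infer that the rule contradicts the statement that AESI are identified before unblinding. It does not do so directly. Participants with a confirmed pregnancy are individually unblinded (sections 2.7.4 and 4.3), so their arm can be known before the study as a whole is unblinded. The issue is selection with knowledge of the arm.

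Nor does the SAP discard the TDF/FTC pregnancies. Section 9.2 requires reporting by arm, summarizes adverse events by treatment group and lists them all by subject. Section 7.3.7 d tabulates pregnancy outcomes by arm without any CAB-based term selection. That confines the problem to one descriptive summary, but presenting results by arm does not correct terms chosen from one arm.

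Finally, the comparison has limits of its own. Women who become pregnant are a post-randomization subset, section 7.3.2 plans no routine formal test for individual event types, and section 9.2 calls safety reporting descriptive. All of this stands and limits the weight of the point.

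**Conclusion.** The point holds in a limited form. The pregnancy AESI has no term list, no stated data source and no TDF/FTC-side source, and its only stated origin is exposure to one product. That departs from the arm-neutral definitions in the rest of Appendix E, and the broken pointer to the AESI methods supplies no correcting rule.

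Whether counts are actually distorted depends on assumptions A and B in the working. The tag for this trial and the missing list suggest A, but the SAP does not state it. If both hold, descriptive counts tilt against CAB. With equal means the ratio is about 2.5 at 0.5 events per term per arm and 1.2 at 2 events. It is smaller when term frequencies vary and negligible for common terms. These sizes are illustrative, since the SAP gives no counts. The primary efficacy and safety analyses, the pregnancy incidence and outcome tables and the overall adverse event tables do not use these terms and are unaffected.

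**What to change.** Define the pregnancy AESI term set without regard to arm, in one of two ways:
- a preferred-term list printed in Appendix E, fixed in advance, with its source stated; or
- all adverse events with onset from the first positive pregnancy test to the pregnancy outcome, in pregnancies of either arm.

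Tabulate by arm using the same terms. Show drug exposure at conception and during pregnancy as a sub-classification within the table, not as the rule for choosing terms. State that the comparison is descriptive because pregnancy occurs after randomization. Repair the broken reference to the AESI analysis section.

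The cost is SAP wording and table layout. Pregnancies are already followed in both arms (section 2.7.4), and drug exposure is already to be tabulated (section 7.3.7 d).

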Although not pre-specified as an AESI, further analysis of pyrexia and related terms (Pyrexia Plus), sciatica and specific musculoskeletal related terms, and pancreatitis and related terms (Pancreatitis Plus) will be conducted, based on regulatory interest in the treatment indication, in order to characterise these phenomena in the PrEP population.

The following preferred terms have been identified for these areas of interest:

Pyrexia Plus includes PT: (Chills – 10008531, Feeling of Body Temperature Change - 10061458, Feeling Hot - 10016334, Body Temperature Increased - 10005911, Pyrexia - 10037660, Influenza Like Illness - 10022004, Fever – 10016558).

Sciatica PT: (Sciatica - 10039674) and specific Musculoskeletal includes PT: (Back pain – 10003988, Myalgia – 10028411, Pain in extremity – 10033425, Musculoskeletal pain - 10028391).

Pancreatitis Plus includes PT: (Pancreatitis - 10033645, Pancreatic enzymes increased - 10061900, Abdominal pain - 10000081, Abdominal pain upper - 10000087, Abdominal discomfort - 10000059, Nausea - 10028813). When looking at Pancreatitis Plus events after elevated lipase, the elevated lipase is defined as lipase above the upper limit of normal (ULN).

Section 1: AE Preferred Term for AESI identification (based on MedDRA v23.1)

Hepatotoxicity (Hepatic failure, fibrosis and cirrhosis and other liver damage-related conditions)

PT	PT Code
Acquired hepatocerebral degeneration	10080860
Acute hepatic failure	10000804
Acute on chronic liver failure	10077305
Acute yellow liver atrophy	10070815
Ascites	10003445
Asterixis	10003547
Bacterascites	10068547
Biliary cirrhosis	10004659
Biliary fibrosis	10004664
Cardiohepatic syndrome	10082480

Cholestatic liver injury	10067969
Chronic hepatic failure	10057573
Coma hepatic	10010075
Cryptogenic cirrhosis	10063075
Diabetic hepatopathy	10071265
Drug-induced liver injury	10072268
Duodenal varices	10051010
Flood syndrome	10084797
Gallbladder varices	10072319
Gastric variceal injection	10076237
Gastric variceal ligation	10076238
Gastric varices	10051012
Gastric varices haemorrhage	10057572
Gastrooesophageal variceal haemorrhage prophylaxis	10066597
Hepatectomy	10061997
Hepatic atrophy	10019637
Hepatic calcification	10065274
Hepatic cirrhosis	10019641
Hepatic encephalopathy	10019660
Hepatic encephalopathy prophylaxis	10066599
Hepatic failure	10019663
Hepatic fibrosis	10019668
Hepatic hydrothorax	10067365
Hepatic infiltration eosinophilic	10064668
Hepatic lesion	10061998

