Convulsion in childhood	10052391
Convulsions local	10010920
Convulsive threshold lowered	10010927
CSWS syndrome	10078827
Deja vu	10012177
Double cortex syndrome	10073490
Dreamy state	10013634
Drug withdrawal convulsions	10013752
Early infantile epileptic encephalopathy with burst-suppression	10071545
Eclampsia	10014129
Epilepsy	10015037
Epilepsy surgery	10079824
Epilepsy with myoclonic-ataxic seizures	10081179
Epileptic aura	10015049
Epileptic psychosis	10059232
Faciobrachial dystonic seizure	10084187
Febrile convulsion	10016284
Febrile infection-related epilepsy syndrome	10079438
Focal dyscognitive seizures	10079424
Frontal lobe epilepsy	10049424
Gelastic seizure	10082918
Generalised onset non-motor seizure	10083376
Generalised tonic-clonic seizure	10018100

Glucose transporter type 1 deficiency syndrome	10078727
GM2 gangliosidosis	10083933
Grey matter heterotopia	10082084
Hemimegalencephaly	10078100
Hyperglycaemic seizure	10071394
Hypocalcaemic seizure	10072456
Hypoglycaemic seizure	10048803
Hyponatraemic seizure	10073183
Idiopathic generalised epilepsy	10071081
Infantile spasms	10021750
Jeavons syndrome	10084303
Juvenile myoclonic epilepsy	10071082
Lafora's myoclonic epilepsy	10054030
Lennox-Gastaut syndrome	10048816
Migraine-triggered seizure	10076676
Molybdenum cofactor deficiency	10069687
Multiple subpial transection	10079825
Myoclonic epilepsy	10054859
Myoclonic epilepsy and ragged-red fibres	10069825
Neonatal epileptic seizure	10082068
Neonatal seizure	10082067
Partial seizures	10061334
Partial seizures with secondary generalisation	10056209

Petit mal epilepsy	10034759
Polymicrogyria	10073489
Post stroke epilepsy	10076982
Post stroke seizure	10076981
Postictal headache	10052470
Postictal paralysis	10052469
Postictal psychosis	10070669
Postictal state	10048727
Post-traumatic epilepsy	10036312
Schizencephaly	10073487
Seizure	10039906
Seizure anoxic	10039907
Seizure cluster	10071350
Seizure like phenomena	10071048
Severe myoclonic epilepsy of infancy	10073677
Simple partial seizures	10040703
Status epilepticus	10041962
Sudden unexplained death in epilepsy	10063894
Temporal lobe epilepsy	10043209
Tonic clonic movements	10051171
Tonic convulsion	10043994
Tonic posturing	10075125
Topectomy	10073488

Transient epileptic amnesia	10081728
Tuberous sclerosis complex	10080584
Uncinate fits	10045476
Confusional state	10010305
Loss of consciousness	10024855
Syncope	10042772
Sopor	10058709
Stupor	10042264
Altered state of consciousness	10050093

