Depressed level of consciousness	10012373
Consciousness fluctuating	10050093

Weight Gain

PT	PT Code
Abdominal fat apron	10077983
Overweight	10033307
Abnormal weight gain	10000188
Central obesity	10065941
Obesity	10029883
Weight abnormal	10056814
Weight increased	10047899
Waist circumference increased	10064863
Body mass index abnormal	10074506
Body mass index increased	10005897
Fat tissue increased	10016251
Sarcopenic obesity	10083992

Rhabdomyolysis

PT	PT Code
Muscle necrosis	10028320
Myoglobin blood increased	10028625
Myoglobin blood present	10059888
Myoglobin urine present	10028631
Myoglobinaemia	10058735
Myoglobinuria	10028629
Myopathy	10028641
Myopathy toxic	10028648
Necrotising myositis	10074769
Rhabdomyolysis	10039020
Thyrotoxic myopathy	10081524
Myalgia	10028411
Myositis	10028653

Pancreatitis

PT	PT Code
Cullen's sign	10059029
Grey Turner's sign	10075426
Haemorrhagic necrotic pancreatitis	10076058
Hereditary pancreatitis	10056976
Immune-mediated pancreatitis	10083072
Ischaemic pancreatitis	10066127
Oedematous pancreatitis	10052400
Pancreatic abscess	10048984
Pancreatic cyst drainage	10082531

Pancreatic haemorrhage	10033625
Pancreatic necrosis	10058096
Pancreatic phlegmon	10056975
Pancreatic pseudoaneurysm	10081762
Pancreatic pseudocyst	10033635
Pancreatic pseudocyst drainage	10033636
Pancreatic pseudocyst haemorrhage	10083813
Pancreatic pseudocyst rupture	10083811
Pancreatitis	10033645
Pancreatitis acute	10033647
Pancreatitis haemorrhagic	10033650
Pancreatitis necrotising	10033654
Pancreatitis relapsing	10033657
Pancreatorenal syndrome	10056277
Subacute pancreatitis	10084554

Impact on Creatinine

PT	PT Code
Acute kidney injury	10069339
Acute phosphate nephropathy	10069688
Anuria	10002847
Azotaemia	10003885
Continuous haemodiafiltration	10066338
Dialysis	10061105
Foetal renal impairment	10078987
Haemodialysis	10018875
Haemofiltration	10053090

Neonatal anuria	10049778
Nephropathy toxic	10029155
Oliguria	10030302
Peritoneal dialysis	10034660
Prerenal failure	10072370
Renal failure	10038435
Renal failure neonatal	10038447
Renal impairment	10062237
Renal impairment neonatal	10049776
Subacute kidney injury	10081980
Atypical haemolytic uraemic syndrome	10079840
Cardiorenal syndrome	10068230
Chronic kidney disease	10064848
Crush syndrome	10050702
Diabetic end stage renal disease	10012660
End stage renal disease	10077512
Foetal renal impairment	10078987
Haemolytic uraemic syndrome	10018932
Hepatorenal failure	10019845
Hepatorenal syndrome	10019846

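### Appendix E gives MedDRA code 10050093 to two different terms in the seizure list, so at least one code is wrong, and the SAP does not say whether AESI are matched on term or on code

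*SAP*

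**What the plan says.** Appendix E of the SAP defines the adverse events of special interest (AESI) through lists of terms, under the heading "Section 1: AE Preferred Term for AESI identification (based on MedDRA v23.1". Each list has two columns, the preferred term (PT) and its PT code. The Seizures/Convulsions list ends with eight terms on altered consciousness. The last three are, in order:

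- "Altered state of consciousness 10050093"
- "Depressed level of consciousness 10012373"
- "Consciousness fluctuating 10050093"

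The first and third carry the same code.

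On how AESI are found, the appendix says: "The identification and classification of AESI will have occurred as a clinical review of preferred terms for adverse events, lab data, ECG and vital signs". It does not say whether the programs that flag AESI compare the term or the code. It refers to another section for details of the AESI analyses, but in the text at hand that cross-reference does not resolve, so the rule cannot be looked up there.

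**The concern.** A PT code serves as the identifier of one preferred term, and two different terms cannot share it. The duplicate therefore shows, without any outside source, that the list contains an error.

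Seizures and seizure-like events are a named AESI for cabotegravir, included for clinical and regulatory interest (Appendix E, Table 1), and the list is the SAP's working definition of that group. Section 10.2 describes Version 4.0 as containing corrections and detail for programming the Clinical Study Report, and item 10.2.1 restores this appendix after it had been cut short. A programmer could reasonably copy the code column into a lookup. In that case events of the miscoded term would not be flagged, and the AESI summary would cover fewer terms than the list promises.

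**Working it through.** The SAP states no figure to reproduce here. The check is a count of terms and codes, followed by the consequences under each matching rule.

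**1. Inputs.** All rows of the Seizures/Convulsions list in Appendix E, Section 1, from *1p36 deletion syndrome* to *Consciousness fluctuating*.

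**2. Count.** If every term had its own code, the number of distinct codes would equal the number of distinct terms.

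- Rows: 100
- Distinct terms: 100
- Distinct codes: 99
- Difference: 100 − 99 = 1

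The single shortfall is code 10050093, attached to *Altered state of consciousness* and to *Consciousness fluctuating*. No other code in the list is attached to two terms.

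**3. Is it an artefact of reading the PDF?** Unlikely. Both rows are complete, and an intact row with a different code, "Depressed level of consciousness 10012373", stands between them. A split or shifted table row would not leave that pattern.

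**4. Does the SAP otherwise keep one code per term?** Terms that appear in more than one list keep their code:

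| Term | Code | Lists |
|---|---|---|
| Sopor | 10058709 | Sleep Disorders; Seizures/Convulsions |
| Stupor | 10042264 | Sleep Disorders; Seizures/Convulsions |
| Myalgia | 10028411 | Rhabdomyolysis; Musculoskeletal Events |

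So the appendix itself treats a code as belonging to one term, and the shared code breaks its own pattern.

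**5. Consequence by matching rule.**

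| AESI flag programmed on | Which code is wrong | Listed terms not captured |
|---|---|---|
| Term | either or both | 0 of 100 |
| Code | one of the two | 1 of 100 |
| Code | both | 2 of 100 |

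These are shares of terms, not of events. The SAP gives no expected frequency for either term, so no number of lost events can be derived.

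**The case against.** The strongest reply is that the text points to terms, not codes. The list is headed as preferred terms for identification, the appendix describes a clinical review of preferred terms, and Section 9.2 summarises adverse events by system organ class and preferred term. Both disputed terms are on the list by name, so matching on the term captures both. That stands, and it limits the point.

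Two stronger readings are tempting, and the documents do not support them.

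- A reader might infer that the code column is the selection key and that one term's events will certainly be lost. No part of the SAP says so. The loss occurs only if the programs match on code.
- A reader might infer that such events would disappear from safety reporting. They would not. Section 9.2 requires all adverse events to be tabulated by preferred term and listed by participant with verbatim and preferred terms. At worst an event is missing from one AESI grouping.

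It is also true that the AESI output is descriptive. The primary safety comparison in Section 7.3.2 rests on all adverse events of maximum grade 2 or higher, not on AESI flags, and the primary efficacy analysis does not use these lists.

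What does not stand is that the error can be left alone. The SAP permits matching on code, the list fails under that choice, and the list was issued for programming.

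**Conclusion.** The point holds as a minor correction. Code 10050093 is given to two different preferred terms in the Seizures/Convulsions list, so at least one of the two entries is wrong. The SAP does not show which, and both could be.

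The size is one shared code in a list of 100 terms. Matching on code would leave out one listed term, or two if both codes are wrong. Matching on term would leave out none. The effect is confined to the descriptive seizure and seizure-like AESI summary, and the number of events affected may be zero.

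The conclusion rests on two assumptions: that a PT code identifies one preferred term, which the appendix's own recurring terms bear out, and that the rows stand in the source as they were read, which their completeness supports.

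**What to change.** 1. Look up *Altered state of consciousness* and *Consciousness fluctuating* in MedDRA v23.1, the version that the appendix names, and correct the wrong code or codes.
2. Add one sentence to Appendix E stating that AESI matching uses the preferred term or, if preferred, the corrected code.
3. Before programming, run a check over all Appendix E lists that each term carries exactly one code and each code belongs to exactly one term.

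The cost is two dictionary lookups, one sentence and one short programming check. It needs no new data and changes no planned analysis.
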